8. INTERVENTIONS / INVESTIGATIONS

For all participants in the two groups, investigation will consist in 1 URDT (Malaria Ag P.f ultrasensitive, SD/Alere, Republic of Korea).

For *P. falciparum* URDT positive individuals in the two groups:

- collection of 3x1cm dried blood spots on filter paper
- administration of a supervised antimalarial treatment course to individuals for which a *P. falciparum* will have been detected by URDT.

Specifically in **group 1**, a population list will be collected in each village prior to MSAT campaign and all participants will undergo:

- collection of a 50µL-aliquot of capillary blood for each participant to the screening during the MSAT intervention.
- 1 URDT + collection of a 50µL-aliquot of capillary blood for each participant to the follow-up survey at M12.

A safe, recommended treatment of *P. falciparum* malaria will be administered to URDT positive individuals based on participant's characteristics:

- The standard regimen for participants without known antimalarial allergy, not pregnant and not breastfeeding, will be a 3-day supervised weight-adjusted DP course and a single low dose PMQ. The single low dose PMQ will be administered on the first day.
- Pregnant women and in their 2nd or 3rd trimester, and breastfeeding mothers, will receive a DP course but no PMQ.
- Pregnant women in their first trimester will receive an oral course of quinine+clindamycin (7 days).
- Individuals with known drug allergy to piperaquine will be treated with AL (+/- sld PMQ as per their pregnancy/breastfeeding status)
- Specific/complex cases will be assessed by a medic and referred to a health facility for treatment if necessary.

The treatment will be directly observed by the MSAT team.

9. STATISTICS AND ANALYSIS

9.1. Description of Statistical Methods

Coverage of intervention: the coverage of the intervention will be defined as the proportion of individuals screened by URDT divided by the total number of individuals present in the village during the next

Before/after MSAT yearly cumulative incidence and 95% Poisson confidence intervals will be calculated using:

- Numerator: the total number of *P. falciparum* cases reported during the weeks with an MP report.
- Denominator: the village population size measured during the MSAT * number of weeks with an MP report during the year (number of weeks of MP activity).

Analysis including the entire follow-up available for malaria posts will be conducted in order to provide adjusted estimates on the

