Figure 3: Average *P. falciparum* and *P. vivax* incidence in hotspots before and after MDA, centered on date of MDA. A marked decrease in *P. falciparum* incidence after MDA can be observed, in spite of an increase in incidence around 15 months after MDA. This increase is related to 5 hotspots (out of 52 followed up to M18) showing an incidence above 50 case/1000 for 1 month during the second year after MDA. This increase did not persist further.

In this project, we aim at an operational research deployment of URDT-based MSAT in the METF elimination program. This intervention will be tested in two types of setting, which correspond to two arms in this study. In group 1, MSAT will be used in a programmatic setting in order to decrease the reservoir of asymptomatic carriers in high incidence villages (following the same principles and objective as previously deployed MDA interventions). In group 2, we take advantage of the lighter framework of MSAT to use it as a reactive intervention in order to respond to malaria outbreaks in low to intermediate incidence villages. The MSAT intervention will be preceded with community-level consent and community engagement (CE) activities. MSAT will be conducted over a period of approximately 1 week in each hamlet, village or group of villages, and will consist in administering a *P. falciparum* URDT to all individuals agreeing to participate. A limited subgroup (expected 5-25%) will be found positive and receive supervised treatment over 3 days for the standard regimen (DP to cure asexual stage infection + single low-dose primaquine to destroy gametocytes). After this intervention, the incidence of clinical falciparum episodes will be monitored by the village MP. In group 1, a comparison of the prevalence at baseline and 12 months after MSAT intervention will be performed through a second URDT survey, in addition to which both baseline and 12-month surveys will include the collection of a 50 μ L capillary blood sample for reference detection in the laboratory.

The intervention will be evaluated primarily on its ability to reduce yearly cumulative incidence of clinical falciparum malaria compared to year before intervention. Additional evaluations of the impact of MSAT will include: in group 1, comparison of asymptomatic infection prevalence; and in group 2, modifications of the shape of the incidence curve following intervention.

Potential risks and benefits for participants

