7.5. Baseline Assessments

The baseline assessment (D0) will occur immediately after inclusion. Participants will be asked baseline demographic data (age, sex, visitor status, occupation and activities during the previous month) and baseline clinical data (temperature and history of fever over the previous week), which will be recorded in a logbook where each patient will be identified by a unique number printed on a sticker that will also be used to label the URDT, the sample(s) collected from the participant.

In **group 1 only**, participants will undergo a finger-prick from which capillary blood will be collected using the lancet provided by the URDT manufacturer in order to realize the URDT. From the same finger-prick, 50 μ L of capillary blood will also be collected on an EDTA microtube, labelled with a participant sticker.

The URDT will be read by a trained field worker following the manufacturer's instructions. If the test is positive, a second finger prick will be conducted in order to collect an additional blood sample on filter paper (3x 1cm blood spots), labelled with a participant sticker.

If the test is positive, a physical and clinical examination will be conducted. Female participants of child-bearing age will be asked if they are or could be pregnant and proposed to take a pregnancy test if unsure. History of malaria diagnosis and treatment during the previous week will be collected. The weight of the participant will be measured and history of previous allergies to drugs and specifically antimalarials will be collected. A curative treatment for *P. falciparum* malaria will be administered to falciparum-positive participant following a weight-adjusted dosage and according to each participant characteristics (see 8. intervention).

The willingness and ability of eligible participants to take a complete treatment will be assessed by the fieldworker, and the importance of completing the treatment will be discussed with the participant if

necessary. The first dose of treatment will be administered directly, and recorded in the logbook. An appointment will be set for the next dose on the following day.

Participants who declare being unable to attend supervised treatment for the next takes will be given the remaining doses (expected <2.5% of treatments initiated).

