7.6.2. Malaria incidence monitoring

Each village is equipped with a community-based malaria post, where a trained member of the community provides diagnosis and treatment to all fever cases occurring in the village. The MP records the result of all RDT conducted and reports weekly activity data, including number of fever consultations, number and result of RDT performed and number of clinical malaria episodes treated by sex and age-group of patient and by parasite species.

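### The MSAT week is left in the incidence series although the MSAT team, not the malaria post, treats and logs the positives it finds; it should be handled as a transition period

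*Combined protocol and SAP*

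**What the plan says.** **Case counting.** Section 9.1 takes as numerator the *P. falciparum* "cases reported during the weeks with an MP report". The denominator is village population multiplied by the "number of weeks with an MP report during the year (number of weeks of MP activity"). Section 7.6.2 says where these counts arise: "The MP records the result of all RDT conducted and reports weekly activity data".

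**What happens during MSAT.** Section 3 states: "MSAT will be conducted over a period of approximately 1 week in each hamlet, village or group of villages". Section 6.3.2 does not exclude people with fever. Section 7.5 collects "baseline clinical data (temperature and history of fever over the previous week), which will be recorded in a logbook", and for positives: "The first dose of treatment will be administered directly, and recorded in the logbook". Section 8 has the MSAT team observe the treatment.

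**Place of the MSAT week in the analysis.** Section 9.3 uses a two-year weekly series, one year on each side of MSAT, with MSAT as a binary term. It does not say in which week the term switches. Section 5 speaks of MP recording before and after MSAT and does not mention the week itself. The schedule in Appendix B runs passive incidence collection from Day 0 to Day 365.

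**The concern.** For about one week per cluster, two systems can find and treat a person with clinical falciparum malaria, and only one of them feeds the endpoint. A febrile resident who tests positive with the MSAT team is treated on the spot and entered in the MSAT logbook. No section sends that person to the MP register or adds the logbook entry to the case count. The protocol does name the MP where it intends to use it: for positives at the 12-month survey when prevalence is below 5% (7.6.3), for people who stop study treatment (7.8), and for first-trimester treatment follow-up (7.6.1). It names no such route for ordinary MSAT positives.

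The MP count may therefore fall in that week because cases were diverted and not because transmission fell. The direction of the error depends on a coding choice that the plan leaves open. In the after period, missing cases look like benefit; in the before period they lower the baseline and hide benefit. Threshold-triggered clusters in group 2 are the more exposed, because their MSAT is prompted by a rise in incidence. Group 2 is part of the primary objective in the synopsis.

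**Working it through.** The plan gives no figure for this point, so there is none to reproduce. The check has two parts.

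**1. Is the week in the analysis?** Section 9.1 counts every week with an MP report and states no exclusion. Section 9.3 states none either. Section 4 follows the primary outcome continuously from MP opening to the end of the study, and Appendix B starts incidence collection on Day 0. Taken together, the week is most naturally kept and counted as after. Sections 5 and 9.3 could also be read as leaving it out, in which case the distortion is zero.

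**2. How large could the loss be in group 1?**

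Inputs from 9.2.1: 250 cases/1000/year and 190 inhabitants per village. From section 3: about one week of MSAT. Two assumptions give a ceiling: every case that week is lost, and the week runs at the average baseline rate because MSAT has not yet acted.

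- Cases per village-year: 0.250 × 190 = 47.5
- Cases in the MSAT week: 47.5 / 52 = 0.91, or 1.9% of the year
- Cases in the other 51 weeks at true ratio *r*: *r* × 47.5 × 51/52 = *r* × 46.59

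Week counted as after. Ratio with complete counting = (*r* × 46.59 + 0.91) / 47.5; ratio with the week's cases lost = *r* × 46.59 / 47.5.

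| True ratio *r* | Complete counting | Cases lost | Relative shift |
|---|---|---|---|
| 1 | 1.000 | 0.981 | −1.9% |
| 0.5 | 0.510 | 0.490 | −3.8% |
| 0.2 | 0.215 | 0.196 | −8.9% |

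The last column compares the lost-case ratio with complete counting. Measured against *r* itself, the loss is 46.59/47.5 − 1 = −1.9% in every row. The rest of the gap arises because complete counting puts a week at the untreated rate into the after period (0.215 against 0.2). Excluding the week returns *r* exactly, so it removes both distortions.

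Week counted as before: the baseline becomes 47.5 − 0.91 = 46.59, and the ratio rises by 47.5/46.59 − 1 = +2.0% for any *r*.

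If only half of the week's cases are lost, the shifts roughly halve: −1.0% at the null, −4.5% at *r* = 0.2, +1.0% if before. If MSAT fell at three times the average weekly rate (an assumption), the ceiling against complete counting would be −5.6% at the null, −22.7% at *r* = 0.2, and +6.1% if before.

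**Group 2.** The documents give no counts. The share of the after count that is lost is *m*/(*m* + *n*), with *m* cases in the MSAT week and *n* in the rest of the year. For assumed *m* of 1 to 3 and *n* of 1 to 6, it runs from 1/7 = 14% to 3/4 = 75%. This shows only how sensitive small counts are; it is not an estimate.

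**The case against.** The strongest reply is that the loss is inferred. No section says that febrile positives stay out of the MP register, any more than one says that they enter it. The MP "provides diagnosis and treatment to all fever cases occurring in the village", and nothing suspends that during MSAT. People absent, declining, or falling ill before or after their own screening can still attend. Those treated at the MP in the preceding 7 days are excluded from MSAT (6.3.2) and are already counted. Losing the whole week is therefore a ceiling. **This stands.** A reader might infer that these cases never reach the MP count; the documents support only that no route is provided.

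Second, the plan does not assign the week to either period, and two sentences in 9.1 break off in the available text, so silence there is weak evidence. **This stands in part.** Section 9.3 is complete on this point and still gives no rule, and Appendix B points to inclusion from Day 0.

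Third, the group 1 effect at the null is about 2%, a fifth of the 10% difference in 9.2.1 (25/250). **This stands.**

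Fourth, a reader might infer that every group 2 MSAT falls during an outbreak. Section 9.2 says that many responses follow one case. Even in threshold clusters, investigation (6.1.2.2) and community agreement (7.1) come first, with no stated delay. **This stands**, so no group 2 size can be claimed.

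None of this argues for keeping the week. It limits how much harm can be asserted.

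**Conclusion.** The point holds in a limited form. The endpoint counts MP reports only, a parallel team treats and logs positives for about a week, and the plan neither links the two counts nor sets the week aside. Some clinical cases may be missed, and the sign of the error depends on how the week is coded.

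In group 1 this is small: at most about −2% on the ratio at the null, −9% relative to complete counting at a true ratio of 0.2, or +2% if the week is before. These figures assume the incidence and village size in 9.2.1, an average week, and loss of every case in it. In group 2 the distortion could be material in threshold-triggered clusters (section 5), but the documents do not allow it to be sized. The documents do not support the stronger conclusion that the primary result would be seriously biased. The case for a change is that it is cheap and works whichever way the week would have been coded.

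**What to change.** In 9.1 and 9.3, define each cluster's MSAT week(s) from the campaign's start and end dates, treat them as a transition period, and exclude both their cases and their person-time from the before and the after periods. The binary MSAT term then switches across a gap and no coding choice remains.

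**Cost:** one or two sentences, and about 1 of 104 weeks per cluster (2 of 104 if the campaign straddles two reporting weeks).

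**Optional, as an upper-bound sensitivity analysis only:** keep the week and add febrile URDT-positive participants from the logbook. The data are already collected, but this can overcount for two reasons:

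- URDT finds more infections than RDT. Appendix D gives field sensitivity of 39.6% against 20.9%. With 5% to 25% of 190 people positive (9.5 to 47.5) and an assumed 5% with incidental fever, 0.5 to 2.4 cases would be added, against the 0.9 at issue.
- Section 5 rules out linking individuals to MP cases, so duplicates could not be removed. Section 10.2 nevertheless lists individual clinical case data; the two statements should be reconciled before this analysis is planned.

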7.6.3. Follow-up prevalence survey (group 1)

Twelve months after the beginning of the MSAT campaign in group 1 villages (high incidence), a population list will be collected again and a prevalence survey will be conducted in a sample of village inhabitants to perform URDT and collect a sample of 50µL for reference testing (sample size based on ability to measure a 90% decrease from baseline, see 9.2).

After the subsample of inhabitants has been surveyed, if the URDT prevalence is above 5%, the survey will shift to an MSAT round following the same protocol as baseline. If the URDT prevalence is below 5%, the positive individuals will be referred to MP for treatment and the survey will finish.

This survey will identify households from the MSAT campaign, but not match individual identification codes.

Since the procedures and interventions are similar to

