7.8. Discontinuation/Withdrawal of Participants from Study

The follow-up and study outcomes are defined at the village-level and apply to village populations rather than individuals. An eligible village will be excluded from the study if:

- the MSAT intervention can't be conducted (refused by the community, impossible to access)
- the population size changes by $\geq 50\%$ between MSAT and follow-up survey.

Each participant has the right to withdraw from the study at any time.

In this study, systematic individual follow-up will occur during the MSAT intervention period and after the MSAT intervention to monitor demographics and clinical case incidence.

During the MSAT intervention individual follow-up will be conducted to ensure that a complete treatment is taken by all individuals found infected with *P. falciparum*. In the light of the threats of artemisinin-resistance, it will however be necessary to ensure that all falciparum-positive individuals are treated and that all individuals initiating a treatment take a complete curative course. Counselling will be provided to participants wishing to discontinue their participation. The counsellors will be members of the CE team with an extensive experience of interventions requiring the treatment of asymptomatic participants (filariasis and/or malaria mass drug administration campaigns in the region). In case the participant refuses to continue his/her antimalarial treatment course outside of the study, he/she will be offered to receive standard treatment for falciparum clinical malaria (AL+sld PMQ) from the village MP, or referred to the nearest health facility. The reason for withdrawal will be recorded in the MSAT logbook.

Individuals or households moving in or out of the village will be assessed during the M12 follow-up. Newcomers will contribute to the village follow-up and be included in the prevalence survey if they match inclusion criteria.

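### Section 9.1 divides both the before- and after-MSAT yearly incidence by one population count taken at MSAT, so net population change in group 1 appears as a change in the crude rate although an M12 count is collected

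*Combined protocol and SAP*

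**What the plan says.** Section 9.1 introduces the rates with "Before/after MSAT yearly cumulative incidence and 95% Poisson confidence intervals will be calculated using" and then gives one numerator, "the total number of *P. falciparum* cases reported during the weeks with an MP report", and one denominator: "Denominator: the village population size measured during the MSAT * number of weeks with an MP report during the year". Only the number of reporting weeks can differ between the two years; the population, "the village population size measured during the MSAT", is the same figure in both.

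Section 3 gives this comparison weight. It says that MSAT is judged primarily on its ability to "reduce yearly cumulative incidence of clinical falciparum malaria compared to year before intervention".

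The plan also provides for population change. Under Section 7.6.3, twelve months after MSAT in group 1, "a population list will be collected again"; Appendix B schedules the matching demographic collection at Day 365. Section 7.8 states that "Individuals or households moving in or out of the village will be assessed during the M12 follow-up", and that newcomers count towards the village follow-up. The same section excludes a village if "the population size changes by" 50% or more between MSAT and the follow-up survey.

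Section 9.3 specifies a generalized additive mixed model for the primary incidence rate ratio over 12 months either side of MSAT. It names neither an offset nor a denominator.

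**The concern.** The malaria post counts cases among whoever is living in the village. If people leave after MSAT, cases fall with them while the denominator stays at the MSAT count, and the rate appears to drop. If people arrive, their cases are counted but they are not, and a real benefit is hidden. The plan would record a 40% change at M12, keep the village, and still divide its after-year cases by the old count. Villages are not randomized to a step, so a shared population trend is not balanced by design. At stake is the before/after yearly comparison in group 1 and, if the same denominator is carried into the model, part of the adjusted ratio.

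**Working it through.** **Yardstick.** Section 9.2.1 claims a detectable difference below 25 cases/1000/year from a baseline of 250, which is 25/250 = 10%. A Hussey-Hughes stepped-wedge calculation (60 clusters, 6 steps, 7 periods, variance p(1-p) at p = 0.25, ICC 0.12, two-sided alpha 0.01, the stated beta of 0.9 read as power) gives 19.6/1000 with 190 people per cluster-period. With 190/(1 + 0.49²) it gives 21.9. Both agree with the plan. Counting only 95 person-years per half-year period gives 27.7, which does not. The figure serves here only as a scale.

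**Crude bias.** Let c be the fractional population change from MSAT to M12, with the true rate constant and movers at average risk. The fixed denominator cancels, so

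false rate ratio = mean true population after / mean true population before.

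With a stable before-year this is 1 + c/2 for a linear change and 1 + c for an abrupt change just after MSAT. The documents give no value for c. The range below is an assumption, bounded by what the exclusion rule leaves in.

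| c | Linear: ratio (difference per 1000 at baseline 250) | Abrupt: ratio |
|---|---|---|
| -10% | 0.95 (-12.5) | 0.90 |
| -20% | 0.90 (-25) | 0.80 |
| -40% | 0.80 (-50) | 0.60 |
| -49% | 0.755 (-61) | 0.51 |
| +20% | 1.10 (+25) | 1.20 |
| +49% | 1.245 (+61) | 1.49 |

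Growth masks benefit: a true ratio of 0.80 with 49% linear growth is observed as 0.80 × 1.245 = 0.996.

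**Averaging over villages.** If village changes are independent with mean zero and an assumed SD of 20% (changes of 50% or more removed), the mean ratio is 1.00. The SD of a village's ratio is about 0.095, and over 60 villages the standard error is 0.095/√60 = 0.012. That is noise. Bias in the average needs a net change shared across villages.

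**The adjusted model.** Poisson models were fitted to expected weekly counts, 52 weeks each side of MSAT, with a constant true rate and a fixed denominator.

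| Population change | Step only | Step plus time slope |
|---|---|---|
| Linear fall from MSAT, 20% | 0.90 | 1.00 |
| Linear fall from MSAT, 49% | 0.755 | 0.999 |
| Abrupt fall, 20% | 0.80 | 0.80 |

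A linear fall starting at MSAT is a symmetric hinge, so the time slope leaves a step of about zero. An abrupt fall is itself a step and is not absorbed.

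**Effect of using the M12 count.** The after-year denominator becomes the mean of the two counts.

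- Linear fall of 20% in the after-year only: 0.90/0.90 = 1.00.
- Abrupt fall of 20%: 0.80/0.90 = 0.89, a partial correction.
- Fall of 20% per year through both years: relative to the MSAT count, the population starts at 1/0.8 = 1.25. The before-year mean is 1.125 and the after-year mean is 0.90. The uncorrected ratio is 0.90/1.125 = 0.80; the corrected ratio is 1/1.125 = 0.89.

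**The case against.** The strongest objection is that the Section 9.1 denominator is written for crude yearly rates, whereas the stated primary outcome is an adjusted incidence rate ratio from the Section 9.3 model. A reader might infer that a 20% fall in population would create a false primary effect as large as the claimed detectable difference. The documents do not support that. Section 9.3 names no offset, and the Section 9.1 sentence introducing the adjusted analysis is incomplete in the text available, so carry-over is likely but not written. The model also has a spline for duration of malaria post activity and village-level slopes. If those slopes are on time, they remove nearly all of a gradual change, as the fits above show. This part of the objection stands, with two limits: Section 9.3 does not say which variable the slopes are on, and random slopes are shrunk, so absorption may be incomplete.

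It also stands that 49% is the edge of an exclusion rule and not an expected value, and that changes averaging zero do little to the average ratio.

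A further objection is that the two counts may differ in scope. Section 6.3.1 makes people in temporary settlements nearby eligible at MSAT, while Sections 6.2 and 6.4.2 restrict the M12 survey by length of residence. This is weaker: the restriction governs who is surveyed, not who is listed, and Section 7.8 already compares the two population sizes. It is still a reason to fix one residence definition for both lists.

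**Conclusion.** The concern holds for the crude before/after yearly rates in group 1. As written, the plan turns net population change into a false change in incidence: a ratio of 0.90 for a net linear fall of 20%, 0.80 if abrupt, and equal shifts upward for growth. These figures rest on an assumed common net change, constant true incidence and movers at average risk. No migration figure is available to say which scenario is realistic.

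For the adjusted primary ratio, the supportable conclusion is narrower. The offset is unspecified, a gradual change would probably be absorbed in large part, and an abrupt one would not. It would also be too strong to say that the M12 list solves the problem: it corrects only the after-year, only in group 1, and only partly if the change was abrupt. Nor do these figures argue for keeping villages that changed by 50% or more; that exclusion is a separate design decision.

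**What to change.** - In Section 9.1, for group 1, compute after-MSAT person-weeks from the population interpolated between the M0 and M12 lists over the weeks with a malaria post report, with both lists counted on the same residence definition.
- In Section 9.3, state log person-weeks on this basis as the model offset.
- Report the fixed-M0 denominator as a sensitivity analysis.
- Keep the M0 count for the before-year and for group 2, and state that these remain uncorrected, because no before-year count and no second group 2 count are planned.
- Leave the 50% exclusion rule as it is.

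The cost is a few lines of analysis text; the lists are already scheduled. The downside is the assumption of roughly linear change between the two counts.
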